#### **1.4. Revised Risk Benefit Assessment for Cohorts 3 and 4 – Protocol version 2.0**

Based on the outcomes of an interim analysis of the data collected from the subjects who participated in the first 2 cohorts of the study prior to the temporary halt due to the Covid-19 pandemic, the dose levels and dosing schemes for the subsequent dose cohorts have been revised for version 2.0 of the protocol.

Desentum has reassessed this FIH study for any risks that may be posed to the subjects. Only 2 new cohorts (cohorts 3 and 4), of similar size and composition as the originally planned 4 additional cohorts (cohorts 3-6), will be included with doses and dose escalation schemes substantially modified. The dose escalation schemes in cohorts 3 and 4 will provide information about the safety of repeated dosing on a bi-weekly basis, as well as on the development of desired immunological responses, both regarded as essential information for planning of phase II dose finding studies where the preliminary efficacy of DM-101 will be studied.

Based on the interim results from the cohort 1 and 2 subjects, transient, mild injection site reactions may occur with the doses selected for cohorts 3 and 4, but major safety risks are not anticipated. Systemic allergic reactions were reported in cohort 2, but none was reported following injection of the dose of 100 ng. Administration of doses above 100 ng per s.c. injection are not planned in the amended dosing regimen. It is acknowledged that s.c. AIT is associated with a low risk of reversible, systemic allergic reactions, mostly occurring within an hour following treatment administration (Kannan, 2013; James, 2017; Nurmatov, 2017). The use of standardized allergen extract products and rigorous practices of surveillance have made the risk for life-threatening reactions extremely small (Makatsori, 2014; Caminati, 2015). Nevertheless, the study involves risks and the potential development of local and systemic allergic reactions after dosing with DM-101 will be thoroughly monitored.

Specific risk management measures include the following:

- Only subjects in good general health and with no previous history of anaphylaxis, moderate to severe or uncontrolled asthma, or immunologic or other major disorders will participate in this study (see Inclusion/Exclusion Criteria, Section 4.2).
- The treatment phase of the study will be conducted out of the local birch pollen allergy season to reduce any potential risk from additional natural allergen exposure.
- The study will be undertaken at a clinical research unit with previous experience in FIH clinical trials and good understanding of the associated safety risks. The study team has all required facilities and knowledge how to handle medical emergencies, including severe, systemic allergic reactions, and collaborates closely with Turku University Hospital and its Intensive Care Unit (ICU). All dosing

visits of cohorts 3 and 4 will take place within the premises of Turku University Hospital, in its Emergency Care Unit. The subjects will be confined in the Unit for at least 6 h after the dosing. A qualified physician will be present at the site throughout the confinement periods of the study subjects.

- The DM-101 doses proposed for evaluation in cohorts 3 and 4 have been selected based on careful analysis of the interim results of cohort 1 and 2 subjects of this study and additional in vitro research carried out after study initiation.
- Treatment administration in each dosing cohort will follow a carefully staggered schedule to assure minimal exposure to the IMP, until preliminary clinical safety data have been collected. The staggered dosing schedule for each cohort is described in detail in Section 3.2. In addition, cautious criteria have been set to stop further administration of the IMP, in case of significant AEs (see Section 9).
- The starting dose (30 ng) of cohorts 3 and 4 has been found to be safe in the first part of this study (cohort 1). The planned dose escalation with biweekly dosing involves only very modest dose escalation. In cohort 3, all doses to be administered (30-100 ng) have already been administered as starting doses in cohorts 1 and 2 of the study without systemic allergic reactions. Progression of dose escalation above 100 ng in cohort 4 will take place only after completion of the 4th dosing of cohort 3 and favorable recommendation from the study's Safety Review Committee (SRC), after its review of all available safety data (see Section 3.2).
- Daily doses greater than 100 ng will be divided into separate injections with a dose of 100 ng in each, using at least 30 min intervals between the injections to reduce the risk of systemic allergic reactions.
- During all dosing visits, the subjects will remain under close medical supervision, confined in Turku University Hospital's Emergency Care Unit, until completion of the 6 h assessments after the last injection (see Section 3.2). During this confinement period, a series of clinical and laboratory safety assessments will be performed. Subjects will not be discharged until the Investigator has reviewed the available safety data and finds them satisfactory. The subjects' state of health will be followed up via telephone at approximately 12 and 24 h after completion of the dosing. Furthermore, all subjects will be provided with detailed written instructions, rescue medication (adrenaline autoinjector) and an action plan on what to do in case of a late-appearing systemic allergic reaction.

Based on the interim results of cohorts 1 and 2 of this study, it is considered that the estimated risk-benefit ratio is appropriate for the continuation of this FIH study according to the revised study protocol (version 2.0).

## **2. STUDY OBJECTIVES AND ENDPOINTS**

### **2.1. Objectives**

#### **2.1.1. Primary Objective**

To evaluate the safety and tolerability of s.c. administration of DM-101 in adult subjects with birch pollen allergy.

#### **2.1.2. Secondary Objective**

To determine the proportion of adult subjects with birch pollen allergy who reach the pre-defined, maximum admissible s.c. DM-101 dose in each dosing group.

#### **2.1.3. Exploratory Objective**

To evaluate the possible effects of repeated s.c. DM-101 dosing on immunological biomarkers in adult subjects with birch pollen allergy.

### **2.2. Endpoints**

#### **2.2.1. Primary Endpoint**

The number of all Treatment Emergent Adverse Events (TEAE) in subjects receiving s.c. DM-101, compared to placebo.

#### **2.2.2. Secondary Endpoints**

The number and severity of systemic allergic reactions in subjects receiving s.c. DM-101, compared to placebo.

The number and severity of local injection site reactions in subjects receiving s.c. DM-101, compared to placebo.

The proportion of subjects reaching the pre-defined, admissible dose in each DM-101 dosing group.

#### **2.2.3. Exploratory Endpoints**

The effect of repeated s.c. DM-101 dosing on serum levels of birch allergen-specific immunoglobulins, compared to placebo.

The effects of repeated s.c. DM-101 dosing on novel, exploratory immunological biomarkers, compared to placebo.

### 3. STUDY DESIGN

#### 3.1. Overview

This will be a randomized, double blind, placebo-controlled, parallel group study to evaluate the safety and tolerability of s.c. administration of DM-101 in subjects with birch pollen-evoked allergic rhinoconjunctivitis. The study will be conducted outside of the birch pollen season in Finland.

The study will include up to 4 cohorts of participants. In each cohort, subjects will be randomly allocated to receive s.c. doses of DM-101 or placebo. Subjects will be allowed to participate in only one cohort and will receive one type of treatment, with either DM-101 or placebo, throughout the study. Cohort 1 of the study included a single dose administration. Cohorts 2 to 4 include repeat dose administration.

Table 2 and 8 describes the type of dosing with DM-101 scheduled to be administered in each cohort of study participants.

The study was started with cohorts 1 and 2, and will now proceed to cohorts 3 and 4 after a substantial protocol amendment. The amended protocol version 2.0 will be followed for the conduct of cohorts 3 and 4. A previous protocol version (1.1) was followed for cohorts 1 and 2.

Dose escalation will be initiated only upon satisfactory review of all available safety data from the previous cohort(s) and favorable recommendation from the study's SRC.

An overall schematic of the study design is presented in Figure 1.

[figure not shown]

Figure 1. Overall Study Design Schematic

### 3.2. Study Periods

Study participation includes a screening period, a treatment period and a follow-up period.

#### **Screening Period:**

Up to 2 months (60 days) prior to treatment randomization, adult subjects with a history of birch pollen-evoked allergic rhinoconjunctivitis will be invited for screening at the clinical research unit (Visit 1). Subjects will first provide informed consent for participation in the trial and may then undergo a preliminary eligibility assessment to confirm their medical history and allergic sensitisation to birch pollen, by skin prick testing (SPT). Subjects with a positive SPT response to birch pollen will then proceed to further medical assessments to determine their eligibility in relation to the study selection criteria. At the discretion of the Investigator, screening evaluations may take place over one or two visits (Visit 1a and Visit 1b).

#### **Treatment Period:**

Once eligibility has been confirmed, subjects will proceed to the treatment period and will be randomly allocated to receive treatment with DM-101 or placebo.

#### **Cohort 1 (completed in accordance with protocol version 1.1)**

Subjects allocated into cohort 1 (Table 2) will visit the clinical research unit (Visit 2) and after a brief medical review will receive a single s.c. injection of DM-101 or placebo. All subjects in this cohort will remain confined in Turku University Hospital's Emergency Care unit until at least 24 h after dosing and will be closely monitored.

Dosing will be staggered in such a way that a sentinel group of 2 subjects, 1 receiving DM-101 and 1 receiving placebo, will be dosed first in a double-blind fashion. Treatment of the remaining subjects in the cohort will be initiated, at the earliest, 22 h after the sentinel subjects have completed their dosing, without safety findings that meet the study's stopping or treatment discontinuation criteria (see Section 9). Subjects in the main treatment group will also receive their doses in a staggered fashion, with 2 subjects receiving their doses first and the remaining subjects being dosed no sooner than 4 h later.

#### **Cohort 2 (started in accordance with protocol version 1.1, discontinued, not to be re-started)**

Initiation of cohort 2 was to take place only after completion of all Visit 2, 24 h post-dosing assessments in all subjects of cohort 1, review of all safety and tolerability data and a favorable recommendation from the study's SRC. There was to be an at least 2 days' interval between completion of the post-dosing 24 h monitoring period in cohort 1 and initiation of dosing in cohort 2.

The study was temporarily halted because of the Covid-19 pandemic after completion of Visit 2 for 1 subject and partial completion of Visit 2 for 4 subjects. Because of the reporting of TEAE of local and systemic allergic reactions in 4 of the 5 participants, the SRC recommended that dosing in the study should not be re-started without a substantial protocol amendment.

## VISIT 2

According to version 1.1 of the study protocol, subjects allocated into cohort 2 (Table 2) were to enter Turku University Hospital's Emergency Care unit and after a brief medical review receive a series of s.c. injections with escalating doses of DM-101 or placebo over 2 consecutive days (Visit 2 Day 1 and Visit 2 Day 2). All subjects in cohort 2 were to remain confined overnight in the hospital and were to be closely monitored until at least 24 h following completion of dosing on Day 2.

Dosing and dose escalation was to be staggered in such a way that 2 sentinel subjects, 1 receiving DM-101 and 1 receiving placebo, were to be dosed first in a double-blind fashion. Dosing of the remaining subjects in the cohort was to be initiated, at the earliest, 22 h after sentinel subjects had completed their Day 2 dosing, without safety findings that would meet the study's stopping or treatment discontinuation criteria (see Section 9). Subjects in the main treatment group were also to receive their doses in a staggered fashion, with 2 subjects starting first to receive doses and the remaining subjects starting to receive doses no sooner than approximately 22 h after the first two subjects of the main group had completed their Day 2 dosing.

Treatment on Day 1 was to start with administration of 100 ng of DM-101 or placebo. This was to be followed by administration of progressively escalating doses of DM-101 or placebo, at approximately 30 min intervals, up to a total of 6 s.c. injections per subject/day. On Day 2, treatment was to start with a repeat of the top DM-101 dose administered on Day 1 or placebo, followed by another 2 administrations of escalating DM-101 doses or placebo, approximately 30 min apart, up to a maximum of 3 s.c. injections per subject/day. Dose escalation, in each subject, was to be allowed only if the study's stopping and treatment discontinuation-adjustment criteria were not met (see Section 9).

## VISITS 3-6

Dosing on Visit 3 was to take place only if there was a favorable recommendation from the SRC, after reviewing of all safety data collected from Visit 2 (Day 1 and Day 2).

The subjects were to return to the hospital 2 weeks ( $\pm$  1 day) after completion of their Visit 2 Day 2 treatment (Visit 3), and after a brief medical review were to receive a single s.c. injection of the last DM-101 dose they were administered on Visit 2 Day 2 (Day 2 injection 3) or placebo. The subjects were to remain confined overnight in Turku University Hospital's Emergency Care unit and were to be discharged only after satisfactory medical review by the attending physician of the clinical research unit, no sooner than approximately 24 h after dosing.

After Visit 3, dosing was to be allowed only if the study's stopping and treatment discontinuation criteria had not been met on the previous dosing visit (see Section 9).

The subjects were to return to the clinical research unit for another 3 visits (Visit 4, Visit 5 and Visit 6). Visit 4 was to take place 2 weeks ( $\pm$  2 days) after Visit 3, followed by Visit 5 and Visit 6, each after another 2 weeks' ( $\pm$  2 days) interval. On each of these visits, subjects were to receive, after a brief medical review, a single s.c. injection of DM-101 or placebo. The dose of DM-101 each subject was to receive was to be the same as that administered on Visit 3. On each of these visits, the subjects were to remain confined in the clinical research

unit for approximately 4 h after dosing and were to be discharged only after satisfactory medical review by the attending study physician. All subjects were to receive a phone call from the clinical research unit, approximately 24 h after discharge, for a brief medical update.

On each of the visits 3 - 6, the sentinel subjects of each cohort were to receive dosing first. The remaining subjects were to receive dosing at least 22 h later. Subjects in the main group were also to receive dosing in a staggered fashion, in such a way that there was to be an at least 30 min interval between each injection.

### **Cohorts 3 and 4**

The revised dosing scheme of protocol version 2.0 will be applied in these cohorts (cohorts 3 and 4). There will be 6 subjects in each cohort allocated to receive s.c. injections of DM-101 and 2 subjects allocated to receive corresponding placebo injections. The recruitment procedures and subject selection criteria have not been modified for version 2.0 of the study protocol.

### **VISIT 2**

Subjects allocated into cohorts 3 and 4 (Table 8) will enter Turku University Hospital's Emergency Care unit, and after a brief medical review and other eligibility assessments they will receive a single s.c. injection of 30 ng of DM-101 or placebo. The subjects will remain confined in the hospital for approximately 6 h following dosing.

Dosing will be staggered in such a way that 2 sentinel subjects, 1 receiving DM-101 and 1 receiving placebo, will be dosed first in a double-blind fashion. Dosing of the remaining subjects in the cohort will be initiated no sooner than 22 h after the sentinel subjects have completed their Visit 2 dosing, without safety findings that would meet the study's stopping or treatment discontinuation criteria (see Section 9). Subjects in the main treatment group in each cohort will also receive treatment in a staggered way, with 2 subjects starting first to receive doses and the remaining subjects starting to receive doses no sooner than approximately 22 h after the first two subjects of the main group have received their Visit 2 dosing.

Visit 2 of cohort 4 subjects will take place after Visit 2 of cohort 3 has been completed.

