Two-week intervals between doses are considered to be long enough for the intended immunological adaptation to develop, to allow dose escalation during the treatment period. This dosing interval was also used in the nonclinical toxicology evaluation of DM-101.

Cohort 4 will not be initiated until cohort 3 Visit 2 has been completed. Dose escalation to doses above 100 ng in cohort 4 will only take place if the review of the collected safety and tolerability data from Visit 5 of cohort 3 is favourable (see Section 3). Repeated dosing and dose escalation within these cohorts will also take place only if safety allows it and the study's dosing discontinuation or adjustment criteria (see Section 9) have not been met.

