### **VISITS 3-6**

After Visit 2, dosing in each cohort will be allowed only if the study's stopping and treatment discontinuation criteria have not been met on the previous dosing visit (see Section 9).

All subjects will return to the hospital for another 4 visits (Visit 3, Visit 4, Visit 5 and Visit 6) on a biweekly basis for the subsequent dosings. In cohort 3, subjects will receive a single s.c. injection on each of these visits. In cohort 4, subjects will receive a single s.c. injection on Visits 3 and 4 and a series of 2 or 3 s.c. injections on Visits 5 and 6, respectively, with a minimum of 30 min interval between subsequent injections. Each injection will be given at a slightly different site of the exterior surface of the upper arm. The injections will alternate between the right and left arm.

Dose escalation to the 200 ng daily dose (Visit 5) in cohort 4 will only take place after a favourable recommendation from the SRC, once it has reviewed all available safety data so far collected in the study, including data from Visit 5 of cohort 3.

On each of the Visits 3-6, dosing will be staggered in the same way as on Visit 2, i.e. 2 sentinel subjects, 1 receiving DM-101 and 1 receiving placebo, will be dosed first in a double-blind fashion. Dosing of the remaining subjects in the cohort will be initiated no sooner than 22 h after the sentinel subjects have completed their dosing, without safety findings that would meet the study's stopping or treatment discontinuation criteria (see Section 9). Subjects in the main treatment group in each cohort will also receive treatment in a staggered way, with 2 subjects starting first to receive doses and the remaining subjects starting to receive doses no sooner than approximately 22 h after the first two subjects of the main group have received their dosing.

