### **Visits 3, 4, 5 and 6**

After Visit 2, all subjects will return to the hospital on a biweekly basis for the subsequent dosings, to receive either a single s.c. injection or a series of 2 or 3 s.c. injections of the study medication. All dosings, except the 4th and 5th dosings of cohort 4, involve only single injections. In cohort 4, the administration of the study medication at Visits 5 and 6 involves 2 and 3 s.c. injections, respectively. There will be a minimum of 30 min interval between subsequent injections. Each injection will be given at a slightly different site of the exterior surface of the upper arm. The injections will alternate between the right and left arm.

On each of the Visits 3-6 dosing will be staggered in the same way as on Visit 2, ie. 2 sentinel subjects, 1 receiving DM-101 and 1 receiving placebo, will be dosed first in a double-blind fashion. Dosing of the remaining subjects in the cohort will be initiated no sooner than 22 h after the sentinel subjects have completed their dosing, without safety findings that would meet the study's stopping or treatment discontinuation criteria (see Section 9).

Subjects in the main treatment group in each cohort will also receive treatment in a staggered way, with 2 subjects starting first to receive doses and the remaining subjects starting to receive doses no sooner than approximately 22 h after the first two subjects of the main group have received their dosing.

Visit 5 dosing of cohort 4 will only take place after a favorable recommendation from the SRC, once it has reviewed all available safety data so far collected in the study, including data from Visit 5 of cohort 3.

Dosing will only be allowed if the study's stopping and treatment discontinuation criteria have not been met.

Subjects will be contacted by telephone approximately 12 and 24 h after completion of dosing for a safety interview after each dosing visit.

Table 12 (for cohort 3) and Table 13 (for cohort 4) (see Section 6.5) show the procedures that will take place, before and after dosing, during the visits. All subjects will remain confined in Turku University Hospital's Emergency Unit for approximately 6 h following their dosing, and may then be discharged if the medical review by the Investigator or a designee is satisfactory.

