## 9.2. Treatment Stopping Criteria

For an individual subject, dosing of study IMP will be discontinued if any of the following happens:

- One Grade 4 systemic allergic reaction according to the WAO classification, following injection of the study IMP.
- Two or more Grade 3 systemic allergic reactions according to the WAO classification, following injection of the study IMP.
- One Grade 4 injection site reaction.
- Two Grade 3 injection site reactions following two injections.
- An AE or need for medication not consistent with the protocol requirements that, in the judgment of the Investigator, presents an unacceptable consequence or risk to the subject.
- Inability or unwillingness to comply with the study protocol or protocol deviation that is considered sufficient to jeopardize the subject's well-being or the integrity of the study.
- Pregnancy during study participation.
- Withdrawal of consent

Discontinuation of dosing will not necessarily result in withdrawal of the subject from the study. For the subjects who discontinue treatment, all safety assessments scheduled for the Follow-up will be requested and observations will be recorded.

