## 9.3. Dose Adjustment Criteria

For each individual subject, dose escalation will be halted and dosing will be adjusted according to the following:

- If a Grade 3 systemic allergic reaction, according to the WAO classification, or a Grade 3 injection site reaction occurs, following administration of a dose of the study IMP, the previous well-tolerated daily dose level should be repeated at the time the next dosing is scheduled. If this is found to be tolerated, the subject will continue to receive the same, tolerated dose level at each subsequent scheduled dosing. Further dose escalation according to the protocol's pre-defined scheme should not be attempted. The number of doses scheduled for one dosing day should not be exceeded.

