- Progression to subsequent dosing cohorts will take place only if the PI's and SRC's review of the collected safety and tolerability data from each preceding cohort is favorable; dose escalation within each cohort will also take place only if safety allows it and the study's dosing discontinuation or adjustment criteria have not been met.

Other possible risks and the measures taken for their mitigation are the following:

- Induction of birch pollen allergy by exposure to DM-101: subjects will be selected based on documented evidence of allergy to the major birch pollen allergen Bet 1 v; thus, exposure to DM-101 should not evoke allergy in a subject not previously sensitized.
- Unexpected findings in any of the evaluations carried out for the purposes of the study: any such incidental findings will be adequately communicated to the subject in question, with appropriate counseling on the need for medical care or follow-up;
- Unexpected AEs related to DM-101, other than allergic in nature: unexpected mechanisms for causation of AEs are always possible in early-phase clinical trials, but their likelihood is small as the employed doses of DM-101 are small (at most, 710 ng), and as repeated dosing of 0.5 mg doses was well tolerated in the GLP toxicity study performed in rabbits. The team will monitor the subjects closely for any unexpected AEs and appropriate measures will be taken, if needed, for their treatment. The measures taken for mitigation of allergy risks are also applicable to other possible AEs.

The subjects will be followed closely for possible AEs and specific dosing interruption criteria are included in the study protocol to ensure subject safety. A SRC will also monitor subject safety and will make recommendations on further dosing and possible modifications to the study.

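### Cohorts 3 and 4: a first Grade 3 systemic reaction in the only active sentinel meets no fixed count in the body-text release rule, while the synopsis states a stricter rule

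*Protocol*

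**What the plan says.** Each of cohorts 3 and 4 has eight subjects, six on DM-101 and two on placebo. Two sentinels, one per arm, are dosed first (Protocol Section 3.2, Cohorts 3 and 4). The rest follow at 22 h or later, provided the sentinels completed dosing "without safety findings that would meet the study's stopping or treatment discontinuation criteria (see Section 9"). Within the main group two subjects go first, and the other four follow "no sooner than approximately 22 h after the first two subjects of the main group have received their Visit 2 dosing". Section 6.3 repeats the rule, and both sections carry it over to Visits 3-6.

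For Visits 3-6, Section 3.2 adds that dosing "will be allowed only if the study's stopping and treatment discontinuation criteria have not been met on the previous dosing visit", and Section 6.3 says "Dosing will only be allowed if the study's stopping and treatment discontinuation criteria have not been met". Neither names the dose adjustment criteria of Section 9.3.

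Three other places read differently:

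- The synopsis (Methodology) states the rule for every cohort as sentinel dosing completed with no safety findings. It gives no threshold and no link to Section 9.
- Section 1.2.3 says: "Repeated dosing and dose escalation within these cohorts will also take place only if safety allows it and the study's dosing discontinuation or adjustment criteria" are not met.
- Section 12 makes dose escalation within a cohort conditional in similar terms: "only if safety allows it and the study's dosing discontinuation or adjustment criteria have not been met".

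Section 9.3 is the only rule with a fixed response to a single Grade 3 reaction ("If a Grade 3 systemic allergic reaction, according to the WAO classification, or a Grade 3 injection site reaction occurs"). It applies to the individual subject, who returns to the previous tolerated dose level.

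**The concern.** Section 12 lists sentinel dosing among the measures that reduce risk to participants. Its value lies in what the rest of the cohort is spared when the sentinel reacts. The protocol treats a Grade 3 systemic reaction as important elsewhere: a history of one from any cause excludes a candidate (Section 4.2.2), and one such reaction ends that subject's own escalation (Section 9.3). Yet the detailed rule that site staff would follow on the day has no fixed response to this event in the one active sentinel. The synopsis appears to require a hold after any finding at all. If the event occurs, two staff members reading different pages could reach opposite decisions about six people.

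**Working it through.** **1. Numbers at risk.** Section 10.1 gives 27 subjects: 6 + 5 + 8 + 8 = 27, which reproduces. No power calculation is claimed. Per cohort, 8 - 2 sentinels = 6 remaining, of whom 6 - 1 = 5 are active and 2 - 1 = 1 is on placebo.

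**2. One Grade 3 systemic reaction in the active sentinel at Visit 2, set against each rule.**

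| Rule | Requirement | Count | Met? |
|---|---|---|---|
| 9.1, study stopping | two Grade 3 systemic reactions, in 2 participants of the cohort | 1 | No |
| 9.2, fixed count | two or more in the same subject | 1 | No |
| 9.2, judgment item | an AE that "in the judgment of the Investigator, presents an unacceptable consequence or risk to the subject" | n/a | Only if the investigator so decides |
| 9.3, adjustment | one Grade 3 reaction | 1 | Yes, but for that subject only, and the release rule does not name it |

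At Visit 2, Section 9.3 also has no previous dose level to return to, because 30 ng is the first dose. A Grade 4 systemic reaction is different: one is enough under both 9.1 and 9.2.

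**3. Timing.** The first two main-group subjects can be dosed from 22 h and the other four from about 22 + 22 = 44 h. Section 8.4.1 requires Grade 2 to 5 systemic reactions to be reported to the Sponsor within 24 h of occurrence. That limit always falls after 22 h. It falls before 44 h for any reaction starting within 44 - 24 = 20 h of dosing. The second follow-up call, at about 24 h (Section 1.4), also comes after 22 h.

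**4. What is known about the risk.** Sections 1.2.3 and 1.4 report no systemic reaction after first doses of 30 ng (4 active, cohort 1) or 100 ng (4 active, cohort 2). The exact upper 95% limit for 0 of n is 1 - 0.025^(1/n):

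- n = 8: 36.9%
- n = 4 (30 ng alone): 60.2%

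There is no systemic signal at these doses, and too few subjects to bound the risk usefully.

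**5. Illustration only.** Assume a Grade 3 risk p per active subject, independent between subjects, and a random order within the main group. The first two then include two active subjects with probability C(5,2)/C(6,2) = 10/15 = 2/3, and one with probability 1/3.

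- Further reaction among the first two: (1/3)p + (2/3)[1 - (1 - p)^2]
- Further reaction among all five active: 1 - (1 - p)^5
- Joint chance per cohort at Visit 2 (sentinel event and a further one): p times the above

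| Assumed p | First two, given a sentinel event | All five, given a sentinel event | Joint, first two | Joint, all five |
|---|---|---|---|---|
| 1% | 1.7% | 4.9% | 0.02% | 0.05% |
| 5% | 8.2% | 22.6% | 0.4% | 1.1% |
| 10% | 16.0% | 41.0% | 1.6% | 4.1% |

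**The case against.** Several points on the other side stand.

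- **The judgment item lies inside the release rule.** It is one of the 9.2 criteria. With no earlier dose to return to, stopping the sentinel under it is a natural course after a Grade 3 systemic reaction at Visit 2, and that would hold the others. But the item concerns risk to the affected subject and is a decision, not a threshold.
- **Other safeguards exist.** They include confinement for 6 h, calls at about 12 and 24 h, an overnight stay or at least 12 h of monitoring after a Grade 3 systemic reaction (Section 8.4.1), and the 24 h report to the Sponsor, whose Medical Monitor sits on the Safety Review Committee (SRC). A second Grade 3 systemic reaction in another participant suspends dosing, so one among the first two main-group subjects would protect the last four. None of these states a hold on the cohort after the first event.
- **The SRC Instructions (Section 3.3) are a separate document, not available here.** They may contain such a rule.

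A reader might infer more than the documents support.

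- **That every hold is discretionary.** The synopsis, read literally, bars main-group dosing after any sentinel finding. The fault is two different rules, not the absence of one.
- **That Sections 1.2.3 and 12 contradict the Visits 3-6 text.** They add criteria which that text omits, but 9.3 works subject by subject, and on that reading there is no conflict. A cohort-wide reading of 1.2.3 would itself clash with 9.3, which lets the subject continue at the earlier dose. The wording is ambiguous; a conflict is not shown.
- **That a Grade 3 injection site reaction should also hold the cohort.** It too meets no fixed count at Visit 2. However, it can be erythema over 10 cm (Table 14), and Table 7 records no severe event in cohort 2 although one subject had two Grade 3 site reactions. A cohort hold for that is debatable and is not proposed here.

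**Conclusion.** The point holds for Grade 3 systemic reactions. Under Sections 3.2 and 6.3, a first isolated one in the active sentinel at Visit 2 meets no fixed criterion. Dosing of up to six further subjects, five of them active, then depends on the 9.2 judgment item, and the synopsis says something stricter. This is a gap and an internal inconsistency in a first-in-human safety rule. It is not evidence that the doses are unsafe.

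The documents give no Grade 3 risk at 30 to 100 ng. The percentages in the illustration rest on assumed risks, and the larger ones are conditional on a sentinel event that may never occur. A reader might take 41% as the risk to the main group; the corresponding joint chance is 4.1%, at an assumed p of 10%. For cohort 4 the evidence at 30 ng will be better, since Visit 2 of cohort 3, with six planned active subjects, is completed first.

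The conclusion assumes that the SRC Instructions add no hold rule. The change is worth making because it alters what happens on the day at little cost.

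**What to change.** Add to the release rule in Sections 3.2 and 6.3, for Visit 2 and for Visits 3-6:

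> If a sentinel subject, or one of the first two main-group subjects, has a Grade 3 systemic allergic reaction at that visit, no further subject in the cohort is dosed at that visit until the Medical Monitor has reviewed the event, blinded, and recorded in writing that dosing may proceed or that the matter is referred to the SRC; the visit window may be extended for the duration of this hold.

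Use the same rule in the synopsis in place of its unqualified condition. State in Sections 1.2.3 and 12 that the adjustment criteria apply per subject. Leave 9.1 and 9.2 unchanged.

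Including the first two main-group subjects matters because a first Grade 3 systemic reaction there is also a count of one and would not hold the last four. Release stays with the Medical Monitor, so this adds a documented pause, not a new stopping threshold.

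The cost is a few sentences of text, with no extra subjects, planned visits or unblinding. Dosing may be delayed briefly, and some visits may fall outside the ±1 day (Visit 3) or ±2 day (Visits 4-6) windows, which the wording allows. At Visit 2 a hold may require a repeat serum pregnancy test, because that test may be no more than 10 days old (Section 6.3).
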